4.1.2 Other Medications

Subjects must be instructed to inform the investigators of the current or planned use or all other medications during the study (including prescription medications, over-the-counter medications, vitamins and herbal and nutritional supplements). It is the responsibility of the investigator to ensure that details regarding all medications are documented. Bisphosphonates started prior to screening activities or initiated during the course of the study to control bone pain may be used with caution.

Colony stimulating factors (*e.g.*, erythropoietin and granulocyte colony-stimulating factors) administered as dictated by safety purposes are acceptable while the subject is enrolled on study.

Pain medications administered as dictated by standard practice are acceptable while the patient is enrolled on the study.

No concurrent investigational agents are permitted.

5 BIOSPECIMEN COLLECTION

5.1 CORRELATIVE STUDIES FOR RESEARCH/PHARMACOKINETIC STUDIES

5.1.1 Peripheral Blood Collection

Subjects will have approximately 70 mL of peripheral blood drawn to evaluate the study drug's effect on the immune response at specific time points during the study and/or after a specified injection. Blood draws will be done at baseline and prior to each injection (baseline, week 6, 14, 30 and EOT).

5.1.2 Samples Collected

Six 10-mL green top sodium heparin tubes for PBMC samples and one 8-mL serum-separating tube for serum samples will be drawn. Samples will be picked up by courier and delivered to the Leidos Biomedical Research facility in Frederick, MD..

5.1.4 Sample Tracking, and Disposition

Samples will be ordered in CRIS and tracked through a Clinical Trial Data Management system. Should a CRIS screen not be available, the CRIS downtime procedures will be followed. Samples will not be sent outside the National Institutes for Health (NIH) without IRB notification and an executed material transfer agreement.

5.1.5 Pharmacodynamic Sample Management and Storage

All data associated with the patient samples is protected by using a secure database. All Clinical Support Laboratory Staff receive annual training in maintaining records' confidentiality. All samples drawn at the NIH Clinical Center will be transported to the Clinical Support Laboratory at the Frederick National Laboratory for Cancer Research by couriers.

Samples will be tracked and managed by Central Repository database, where there is no link to personal identifiable information. All samples will be stored in either a -80°C freezer or vapor phase liquid nitrogen. These freezers are located at NCI Frederick Central Repository in Frederick, Maryland.

NCI Frederick Central Repositories (managed under a subcontract) store, among other things, biological specimens in support of NIH clinical studies. All specimens are stored in secure,

limited-access facilities with sufficient security, backup, and emergency support capability and monitoring to ensure long-term integrity of the specimens for research.

Specimens are stored in accordance with applicable HHS and FDA Protection of Human Subjects Regulations in accordance with the subcontractor's Federal-wide Assurance. The subcontractor's role limited to clinical research databases and repositories containing patient specimens. The subcontractor does not conduct or have any vested interest in research on human subjects, but does provide services and support the efforts of its customers, many of which are involved in research on human subjects. The subcontractor's IRB reviews policies and procedures for labeling, data collection and storage, access, and security. The IRB will review protection of privacy issues prior to acceptance of any new work and in the event of change impacting privacy issues in existing work.

It is the intent and purpose of the subcontractor to accept only de-identified samples and sample information. To the limit of our ability, every effort will be made to ensure that protected information is not sent electronically or by hard copy or on vial labels.

Sample data is stored in the BioSpecimen Inventory System II (BSI). This inventory tracking system is used to manage the storage and retrieval of specimens as well as to maintain specimen data. BSI is designed for controlled, concurrent access. It provides a real-time, multi-user environment for tracking millions of specimens. The system controls how and in what order database updates and searches are performed. This control prevents deadlocks and race conditions. For security, BSI has user password access, 3 types of user access levels, and 36 user permissions (levels of access) that can be set to control access to the system functions. BSI provides audit tracking for processes that are done to specimens including shipping, returning to inventory, aliquoting, thawing, additives, and other processes. BSI tracks the ancestry of specimens as they are aliquoted, as well as discrepancies and discrepancy resolution for specimens received by the repository. If a specimen goes out of the inventory, the system maintains data associated with the withdrawal request. Vials are labeled with a unique BSI ID which is printed in both eye-readable and bar-coded format. No patient-specific information is encoded in this ID.

Investigators are granted view, input, and withdrawal authority only for their specimens. They may not view specimen data or access specimens for which they have not been authorized. Access to specimen storage is confined to repository staff. Visitors to the repositories are escorted by repository staff at all times.

5.1.6 Sample Analysis

Immune assessments will be performed at the Laboratory of Tumor Immunology and Biology at the NCI's Center for Cancer Research (CCR) and include flow cytometry-based and serum assays.

Analyses of PBMCs:

1. Pre- and post-therapy PBMCs, separated by Ficoll-Hypaque density gradient separation, will be analyzed for antigen-specific immune responses using an intracellular cytokine staining assay. PBMCs will be stimulated in vitro with overlapping 15-mer peptide pools encoding the tumor-associated antigens CEA, MUC1, and Brachyury. Control peptide pools will involve the use of human leukocyte antigen peptide as a negative control and CEFT peptide mix as a positive control. CEFT is a mixture of peptides of CMV, Epstein-Barr virus, influenza, and tetanus toxin. Post-stimulation analyses of CD4 and CD8 T cells

will involve the production of IFN- γ , IL-2, tumor necrosis factor, and CD107a. If sufficient PBMCs are available, assays may also be performed for the development of T cells to other tumor-associated antigens. A detailed description of this assay has been previously reported (35).

2. If sufficient PBMCs are available, PBMCs from selected subjects may be analyzed for changes in standard immune cell types (CD4 and CD8 T cells, natural killer [NK] cells, regulatory T cells [Tregs], myeloid-derived suppressor cells [MDSCs], and dendritic cells) as well as 123 immune cell subsets, as described elsewhere (74), and for function of specific immune cell subsets, including CD4 and CD8 T cells, NK cells, Tregs, and MDSCs.

Analyses of soluble factors:

Sera will be analyzed pre- and post-therapy for the following soluble factors: sCD27, sCD40 ligand, and selected patients may be analyzed for cytokines and antibodies to human tumor antigens. For selected patients, sera may be analyzed for antibodies to CEA, MUC1, or Brachyury and adenovirus.

Additional assays:

Blood samples may be used for additional research studies, which may include phenotypic and functional analysis of immune-cell subsets and analyses for cytokines (IFN- γ , IL-10, IL-12, IL-2, IL-4, etc.), chemokines, antibodies, tumor-associated antigens, and/or other markers. In addition, assays for antibody or neutralizing antibody titer to adenovirus (type 5) and cell-mediated immunity to adenoviral antigens may be assessed.

Samples will be tracked according to Section 5.1.4.

5.1.7 Protocol Completion/Sample Destruction

All specimens obtained in the protocol are used as defined in the protocol. Any specimens remaining at the completion of the protocol will be stored in the conditions described above. The study will remain open as long as sample or data analysis continues. Samples will be stored until they are no longer of scientific value or until a subject withdraws consent for their continued use, at which time they will be destroyed. Once primary research objectives for the protocol are achieved, intramural researchers can request access to remaining samples, provided they have an IRB-approved protocol and subject consent or an exemption from the Office of Human Research Protections.

The Investigator will report any loss or destruction of samples to the NCI IRB as soon as he/she is made aware of such loss. The Investigator will report destroyed samples to the IRB if samples become unsalvageable because of environmental factors such as a broken freezer or lack of dry ice in a shipping container, or if a subject withdraws consent. Samples will also be reported as lost if they are lost in transit between facilities or misplaced by a researcher. Freezer problems or lost samples will also be reported to the IRB, the NCI Clinical Director, and the office of the NCI CCR.

6 DATA COLLECTION AND EVALUATION

6.1 DATA COLLECTION

Data will be entered in C3D. The PI will be responsible for overseeing entry of data into an in-house password protected electronic system and ensuring data accuracy, consistency and timeliness. The principal investigator, associate investigators/research nurses and/or a contracted data manager will assist with the data management efforts. All data obtained during the conduct of the protocol will be kept in secure network drives or in approved alternative sites that comply with NIH security standards. Primary and final analyzed data will have identifiers so that research data can be attributed to an individual human subject participant.

All adverse events, including clinically significant abnormal findings on laboratory evaluations, regardless of severity, will be followed until return to baseline or stabilization of event. Patients will be followed for adverse events for a minimum of 30 days after removal from study treatment or until off-study, whichever comes first.

An abnormal laboratory value will be recorded in the database as an AE only if the laboratory abnormality is characterized by any of the following:

- Results in discontinuation from the study
- Is associated with clinical signs or symptoms
- Requires treatment or any other therapeutic intervention
- Is associated with death or another serious adverse event, including hospitalization.
- Is judged by the Investigator to be of significant clinical impact
- If any abnormal laboratory result is considered clinically significant, the investigator will provide details about the action taken with respect to the test drug and about the patient's outcome.

End of study procedures: Data will be stored according to HHS, FDA regulations, and NIH Intramural Records Retention Schedule as applicable.

Loss or destruction of data: Should we become aware that a major breach in our plan to protect subject confidentiality and trial data has occurred, the IRB will be notified.

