3.1.1 Dose Limiting Toxicity

For the purposes of dose escalation a dose limiting toxicity (DLT) is defined as:

- Any Grade 3 or greater toxicity that is possibly related to the vaccine and as defined by Common Terminology Criteria for Adverse Events (CTCAE) Version 5.0 with the exception of transient (≤ 24 hours) Grade 3 flu-like symptoms or fever, which is controlled with medical management or transient (≤ 24 hours) Grade 3 fatigue, skin reactions or rash, headache, nausea, emesis that resolves to Grade ≤ 1 or asymptomatic grade 3 amylase/lipase elevation. For purposes of dose escalation the DLT evaluation period will be for 3 weeks following the first dose of drug.

Subjects experiencing a DLT will be removed from protocol therapy.

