7.2.2 NCI-IRB Requirements for PI Reporting at Continuing Review

The protocol PI will report to the NCI-IRB:

1. A summary of all protocol deviations in a tabular format to include the date the deviation occurred, a brief description of the deviation and any corrective action.
2. A summary of any instances of non-compliance
3. A tabular summary of the following adverse events:
 - All Grade 2 **unexpected** events that are possibly, probably or definitely related to the research;
 - All Grade 3 and 4 events that are possibly, probably or definitely related to the research;
 - All Grade 5 events regardless of attribution;
 - All Serious Events regardless of attribution.

NOTE: Grade 1 events are not required to be reported.

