8.4.6.2 Halting guidelines

The following safety events will trigger a temporary suspension of the study injections:

- Death possibly related to the study agent.
- Two Grade 4 toxicity events that are possibly related to the study agent.
- At any time during the expansion phase > 33% of subjects experience a Grade 3 or 4 major organ toxicity possibly related to study injections.

Assessment of these halting rules is a review of cumulative events for all study participants and should not be confused with reasons for delaying or terminating the treatment schedule of any individual subject.

Treatment may also be suspended for safety concerns other than those described above if, in the judgment of the Investigator, participant safety is threatened

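### Section 6.1 lets a possibly related, asymptomatic, untreated Grade 3-4 laboratory toxicity stay out of the AE database although 3.1.1 can count it as a DLT and 8.4.6.2 as a halting event

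*Combined protocol and SAP*

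**What the plan says.** **Recording rule (6.1, Data Collection).** "An abnormal laboratory value will be recorded in the database as an AE only if the laboratory abnormality is characterized by any of the following". The criteria are discontinuation ("Results in discontinuation from the study"), clinical signs or symptoms, a need for treatment or other intervention, association with death or another serious event, and a judgement criterion ("Is judged by the Investigator to be of significant clinical impact"). No criterion refers to grade.

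**DLT definition (3.1.1).** "Any Grade 3 or greater toxicity that is possibly related to the vaccine and as defined by Common Terminology Criteria for Adverse Events", with a list of exceptions. Most of these are short-lived symptoms. The only laboratory exception is "asymptomatic grade 3 amylase/lipase elevation". Neither symptoms nor clinical impact is a condition for any other laboratory toxicity. On the consequence, 3.1.1 says: "Subjects experiencing a DLT will be removed from protocol therapy".

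**Other uses of graded events.**
- The halting guidelines (8.4.6.2) include "Two Grade 4 toxicity events that are possibly related to the study agent" and, in the expansion phase, a limit on the share of subjects with Grade 3 or 4 major organ toxicity.
- The continuing-review table (7.2.2) asks for "All Grade 3 and 4 events that are possibly, probably or definitely related to the research".
- The safety analysis (8.4.4) tabulates AE frequencies by CTCAE grade.

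**Primary endpoints (1.1.4).** There are three separate items: DLTs with the MTD or highest tested dose; treatment-emergent AEs and SAEs; and clinically significant changes in laboratory tests and other safety measures.

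**The concern.** The rule for what enters the AE database and the rules for what counts as dose-limiting, halting or reportable toxicity use different tests. The first asks about clinical consequence, the others about grade and relatedness. The two sets do not coincide, and the difference runs one way: an exclusion in 6.1 can remove graded laboratory events from AE-based output but cannot add any.

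The direct stake is the AE-by-grade table, which reports a primary endpoint. It could omit Grade 3-4 related laboratory toxicity without any departure from the protocol, and it could then disagree with the DLT count in the same report. The conditional stake is the dose decision and the halting rule, should those counts be compiled from AE entries.

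**Working it through.** The plan gives no figure for this point, so the check is a comparison of the text.

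**Step 1. Test case.** Take a subject with a Grade 3 ALT or neutrophil abnormality on the scheduled week-3 blood sample (Study Calendar, 3.5). It is judged possibly related, causes no symptoms and needs no treatment.

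**Step 2. Apply each section.**

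| Section | Test applied | Test case |
|---|---|---|
| 3.1.1 DLT | Grade 3 or more, possibly related, not excepted | Counts |
| 7.2.2 review table | Grade 3 or 4, at least possibly related | Counts |
| 8.4.6.2 halting | Grade 4, possibly related (two events); or Grade 3-4 major organ toxicity in expansion | A Grade 4 version counts toward the first; the Grade 3 version may count toward the second in expansion |
| 6.1 AE entry | Any listed clinical or administrative criterion | Symptom, treatment and death/SAE criteria not met; see steps 3 and 4 for the other two |
| 8.4.4 AE-by-grade table | Is an AE | Depends on 6.1 |

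The amylase/lipase exception supports this reading of 3.1.1. Exempting one asymptomatic Grade 3 laboratory finding would be unnecessary if asymptomatic laboratory findings did not otherwise count.

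**Step 3. The discontinuation criterion.** It refers to leaving the study, whereas a DLT ends protocol therapy. Section 3.7 keeps the two apart: 3.7.1 lists toxicity under 3.1.1 as a reason to leave therapy, while the off-study list in 3.7.2 contains neither DLT nor toxicity. Read as written, the criterion is not met.

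**Step 4. The clinical-impact criterion.** An investigator could use it, and often would for a recognised DLT. It is discretionary, however, and 3.1.1 has no matching condition, so nothing guarantees entry.

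**Step 5. Other places that might recover the value.**
- Section 7.1.1 treats an abnormal laboratory finding as a possible AE, and 8.4.4 says that all AEs are recorded and tabulated. Both sit in tension with 6.1, which is the more specific rule for data entry.
- The separate laboratory endpoint in 1.1.4 is limited to clinically significant changes, which is close to the same filter.
- Section 8.4.8 says that no individual participant data will be tabulated, so no planned listing would show the value.

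**Step 6. What the count decides.** Under 3.1.2, 1 DLT in 6 leads to expansion and 2 in 6 to de-escalation or, at dose level -1, a possible amendment. 1/6 = 16.7% and 2/6 = 33.3%, against the limit in 8.4.4 of less than 33%. One subject changes the outcome.

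**Step 7. Where the DLT count comes from.** Section 7.6.1 bases dose decisions on toxicity data, and 8.4.4 has DLTs evaluated continuously. Neither names the AE database, the laboratory data or a separate DLT form as the source.

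One dependency: the week-3 sample falls at the end of the three-week DLT period in 3.1.1. Section 8.4.4 gives one week, within which the calendar schedules no post-dose blood test. Those two passages need to be reconciled as well.

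**The case against.** The strongest reply is that 6.1 governs AE entry only. DLTs are a primary endpoint in their own right (1.1.4), they are evaluated continuously (8.4.4), and the team discusses each patient weekly (7.6.1). The halting rules count toxicity events, not database records. A laboratory DLT ends the subject's vaccination, so it would be odd to judge it clinically unimportant. Section 7.2.2 independently requires related Grade 3 and 4 events.

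Much of this stands. It defeats three stronger readings that a reader might draw:

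- **That DLTs will be missed and the wrong dose passed.** No section says that the DLT count is built from AE entries, so this does not follow.
- **That 6.1 turns a grade-based endpoint into a matter of opinion.** The definition in 3.1.1 is untouched by 6.1, and its requirement of possible relatedness is already a judgement.
- **That the earlier ETBX-011 trial gives the size of the effect.** Section 11.1.2 lists one Grade 3 anemia and one Grade 3 alkaline phosphatase increase among 34 patients (2/34 = 5.9%). These are events of any attribution over as many as three doses. Nothing says that they were asymptomatic or untreated, or in different patients. The same section reports no DLT. Turning that rate into a change in the probability of passing a dose would also need a background DLT rate, which the documents do not supply.

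The reply does not rescue the AE-by-grade table. That analysis does rest on AEs, and an omission there would comply with 6.1. Nor does it supply the missing statement of where the DLT and halting counts come from.

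**Conclusion.** The AE recording rule and the toxicity definitions are not aligned. Following 6.1 exactly, a possibly related, asymptomatic, untreated Grade 3-4 laboratory toxicity outside the amylase/lipase exception can be a DLT or contribute to halting, and yet be validly absent from the AE database and from a primary safety table. This rests on the text alone and needs no assumption about event rates.

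Understatement of the DLT or halting count is a further possibility that holds only if those counts are taken from AE entries, which the plan does not say. In that case the direction is known (downward) and the margin is one subject in six. The size cannot be estimated from the documents, because they give neither a rate of related, silent laboratory toxicity for this combination nor the share that investigators would enter under the clinical-impact criterion. Sample size and decision thresholds are not in question.

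**What to change.** 1. Add one criterion to the list in 6.1: the abnormality is CTCAE Grade 3 or higher and at least possibly related to the vaccines.
2. State in 8.4.4 that laboratory DLTs, the laboratory part of the 8.4.6.2 counts and the laboratory grade table are derived from the graded laboratory values as well as from AE entries.

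The scheduled laboratory tests already supply the values, so no extra sampling is needed, and neither the DLT definition nor the decision rule changes. The cost is a few more AE entries and an AE table that may look less favourable. Both changes should be in place before the first dose-level decision.

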6.2 DATA SHARING PLANS

6.2.1 Human Data Sharing Plan

What data will be shared?

I will share human data generated in this research for future research as follows:

- De-identified data in an NIH-funded or approved public repository.
- De-identified data in BTRIS (automatic for activities in the Clinical Center)
- De-identified or identified data with approved outside collaborators under appropriate agreements.

How and where will the data be shared?

Data will be shared through:

- An NIH-funded or approved public repository. Insert name or names: clinicaltrials.gov .
- BTRIS (automatic for activities in the Clinical Center)
- Approved outside collaborators under appropriate individual agreements.
- Publication and/or public presentations.

When will the data be shared?

- Before publication.
- At the time of publication or shortly thereafter.

6.3 EFFICACY ASSESSMENTS

6.3.1 Antitumor Response

Tumor assessments will be done at week 6 and then every 8 weeks thereafter and may include the following evaluations: physical examination (with photograph and measurement of skin lesions, as applicable); cross-sectional imaging using computed tomography (CT) or magnetic resonance imaging (MRI) scan of the chest, abdomen, and pelvis (pelvis scan is optional unless known pelvic disease is present at baseline); nuclear bone scan for subjects with known/suspected bone lesions; and CT or MRI scan of the brain (only as clinically warranted based on symptoms/findings). The preferred method of disease assessment is CT with contrast. If CT with contrast is contraindicated, CT of the chest without contrast and MRI scan of the abdomen/pelvis with contrast is preferred. At baseline, tumor lesions will be selected and categorized as target (measurable disease) or non-target lesions (non-measurable disease).

